6.5 Study Discontinuation

The principal investigator and/or UAB CCC and/or Novartis Pharmaceuticals Corporation and/or AbbVie have the right to terminate the study for any reason, including: the incidence or severity of adverse events indicates potential health hazard for patients, subject enrollment is unsatisfactory; data recording is inaccurate or incomplete, or other reasons discussed with the principal investigator and the UAB CCC.

6.6 Study Parameters

	Pre-Treatment (within 4 weeks of initiation) +/-	Day 1 of each cycle	Day 8 of cycle 1	Day 15 of cycle 1		Every 8 weeks +/-	At Progression +/-	End of Treatment/ Early Termination
Informed Consent	X							
History/Height	X							
Physical Exam/Vital Signs/Weight	X	X					X	X
Performance Status	X	X					X	X
Toxicity Assessment ¹⁰		X					X	X
CBC/Differential/Platelets ¹¹	X	X					X	X
CMP (fasting) ¹¹	X	X					X	X
Magnesium		X						
Concomitant Medications	X	X					X	X
Pregnancy Test ¹	X							
Staging Studies ²	X					X	X	X
Biopsy of a Metastatic Lesion ³	X							
Serum CA27.29 Level	X					X	X	X
Lapatinib Administration ⁷								
Veliparib Administration ⁷								
Pharmacokinetics ⁴		X	X					
ptDNA ^{5,6} and serum ⁵		X	X	X				
Echocardiogram and EKG ⁸	X	X						
Pharmacogenomics ⁹		X						

- 1 Must be obtained within 7 days of initial dosing. Only for patients with childbearing potential.
- 2 Staging studies are defined as studies contributing to response evaluation, e.g. CTs (chest, abdomen, and pelvis), MRI, bone scan, PET, or plain x-rays.
- 3 Mandatory if metastatic site is accessible (see inclusion criteria), i.e. chest wall, breast, skin subcutaneous, superficial lymph node, bone or liver metastases (not lung or brain). Biopsy samples will preferably be obtained using a 14-18 gauge core needle; **at least** two core samples will be obtained and snap frozen and a third sample for the preparation of the paraffin-embedded blocks.
- 4 Samples for the first day will be collected 5 minutes before start of the therapy, 30 and 60 minutes after the first dose of Lapatinib and then 2, 4, 6, 8, and 24 hours after the start of the therapy with Lapatinib, On day 2, patients will take the dose of Lapatinib and Veliparib at the same time of day 1 and samples will be taken 30 and 60 minutes after the first dose of Lapatinib and Veliparib, then 2, 4, 6, 8, and 24 hours. Additional samples will be taken on day 3, before the third day dose of Lapatinib and Veliparib. Same schema will be followed on days 8, 9 and 10. A total of 3-5 mL of blood will be taken at each of the described time points. The actual time of administration of each agent and sample collection should be recorded.
- 5 Blood samples (see Appendix E for ptDNA sampling details) will be obtained from each patient at days 1 (baseline; before the initiation of the research medications), on days 15 and 29 (day 1 of 2nd cycle pre-treatment) of the first cycle. Serum will be obtained (5 ml blood sample) from each patient at days 1 (baseline; before the initiation of research medications), on days 8, 15, and 29 (day 1 of 2nd cycle pretreatment) of the first cycle (serum will be used for evaluation of micro RNA profiling and M30-protein).
- 6 Because shipments of ptDNA samples can only occur on Mondays through Thursdays, initiation of treatment cannot occur on Fridays.
- 7 Patients will receive Lapatinib (1250 mg PO daily continuously) in combination with Veliparib (200 mg PO every 12 hours continuously). A cycle of therapy is defined as 28 days of PO therapy. Lapatinib starts on Day 1 and Veliparib on Day 2.
- 8 Echocardiogram will be obtained every 3 months while on active therapy. EKG will be obtained at baseline, day 2 and 3 of cycle one, and day one of each subsequent cycle. Patients who have a $\geq 20\%$ decrease in left ventricular cardiac ejection fraction relative to baseline, and the ejection fraction is below the institution's lower limit of normal, should have a repeat evaluation of ejection fraction 1-2 weeks later while still receiving investigational product. If the repeat ejection fraction evaluation confirms a $\geq 20\%$ decrease in left ventricular cardiac ejection fraction, and the ejection fraction is below the institution's lower limit of normal, then lapatinib should be temporarily discontinued. If the left ventricular ejection fraction recovers during the next 3 weeks, the patient may be restarted on investigational product at a reduced dose. For such patients, monitoring of left ventricular ejection fraction will then be performed 2 weeks and 4 weeks after rechallenge, and then every 4 weeks thereafter. If repeat ejection fraction evaluation still shows a decrease $\geq 20\%$ in left ventricular ejection fraction relative to baseline, and the value is below the institution's lower limit of normal, then the subject should be withdrawn from investigational product. Patients with an NCI CTCAE grade 3 or 4 LVEF relative decrease must be withdrawn from study medications.
- 9 Blood samples for pharmacogenomic analyses will be collected Cycle 1 Day 1 only before initiation of research agents. Blood will be collected into one 6 ml K2EDTA polypropylene blood collection tube (Becton-Dickinson) and into one PAX gene tube.
- 10 Patients with an NCI CTCAE Grade 3 or 4 interstitial pneumonitis must be withdrawn from study medications.
- 11 Cycle 1, Day1 CBC and CMP only need to be obtained if prior labs are greater than 4 weeks.

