4.1 Inclusion Criteria

- Patients must have pathologically documented breast cancer which is stage IV.
- Tumor must be HER-2-neu negative (defined as 0 or 1+ staining by immunohistochemistry or gene amplification ratio ≤ 2.0 , by FISH), estrogen and progesterone receptors negative (< 1%). Patients with BRCA 1 or 2 mutations will NOT be included.
- Patients must have measurable disease, defined as at least one lesion that can be accurately measured in at least one dimension (longest diameter to be recorded) (RECIST criteria 1.1 – see Appendix D).
- Biopsy of a metastatic lesion is not required for protocol entry but all patients with reasonably accessible lesions (chest wall, breast, skin, subcutaneous, superficial lymph nodes, bones and liver metastases) must agree to biopsy (lung and brain metastasis will not be biopsied):

- Biopsies may be done with local anesthesia or intravenous conscious sedation, according to standard institutional guidelines.
- If a biopsy requires general anesthesia, then it is only allowed if acquisition of tissue is necessary for clinical reasons (i.e. is clinically indicated), and excess tissue that would otherwise have been discarded is then used for research purposes. If a biopsy requires general anesthesia, then a biopsy of that site for research purposes only, *without* a coexisting clinical indication is not allowed on this protocol.
- Patients with reasonably accessible lesions as described above, who will not agree with the biopsy, will not be enrolled in the trial.
- Patients with **NO** reasonably accessible lesions as described above can be enrolled in the trial.
- Prior Therapy:
 - No more than two regimens in the metastatic setting as long as patients have adequate performance status. Patients with no prior chemotherapy for metastatic disease may be included in the trial if they received anthracyclines and taxanes in the adjuvant or neoadjuvant settings. Chemotherapy naïve patients with metastatic disease must have failed anthracyclines and taxanes.
 - Chemotherapy treatment prior to enrollment must be discontinued for at least 3 weeks prior to study entry.
 - Patients must have completed radiation therapy at least 21 days prior to beginning protocol treatment.

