- Patients must have recovered from all reversible toxicities related to prior therapy before beginning protocol treatment, and may not have any pre-existing treatment-related toxicities greater than grade 2. Patients must have < grade 2 pre-existing peripheral neuropathy.
- Patients may receive bisphosphonates; however, if used, bone lesions may not be used for progression or response.
- At least 19 years of age.
- Life expectancy of greater than 12 weeks.
- ECOG performance status ≤ 2 (See Appendix B).
- Patients must have normal organ and marrow function as defined below:
 - Absolute neutrophil count: $\geq 1,000/\mu\text{L}$,
 - Hemoglobin: $\geq 9 \text{ mg/dL}$,
 - Platelets: $\geq 100,000/\mu\text{L}$,
 - Total bilirubin: $\leq 1.5 \times$ institutional upper limit of normal,
 - AST(SGOT)/ALT(SGPT): $\leq 2.5 \times$ institutional upper limit of normal without liver metastases, OR, $\leq 5 \times$ institutional upper limit of normal if documented liver metastases,
 - Creatinine: $\leq 1.5 \text{ mg/dL}$, OR calculated creatinine clearance $\geq 40 \text{ mL/min}$ (calculated by the modified Cockcroft and Gault method).
- Ability to understand and the willingness to sign a written informed consent document.
- Use of an effective means of contraception in subjects of child-bearing potential.
- Negative serum or urine beta-HCG pregnancy test at screening for patients with childbearing potential.
- Ejection fraction must be $\geq 50\%$

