6.2 Pilot Trial

Twenty patients evaluable for response will be entered into this phase pilot trial; they will receive Lapatinib (1250 mg a day continuously for 28 days) in combination with Veliparib 200 mg every 12 hours for 28 consecutive days, starting on Day 2 Cycle 1). No blinding will be used in this study. Patients will be evaluated for response every 2 courses (every 8 weeks) according to the RECIST criteria version 1.1 (see Appendix D). Treatment will be administered on an outpatient basis. Treatment may continue without interruption in patients with CR, PR or SD until progression of the disease or unacceptable toxicity. Patients cannot receive any other concomitant therapy: chemotherapy, targeted therapy, radiation therapy, or other investigational agent while participating in the study. There are some restrictions on concomitant medications which must be recorded (see Appendix H). Patients may receive bisphosphonates; however, if used, bone lesions may not be used for progression or response. Patient with PD at any time will be taken off the study.

Investigators will maintain a confidential screening log of all potential study candidates that includes limited information about the patients (initials, sex, age), date, and outcome of screening process: enrolled in the study, reason for ineligibility or refused to participate. Investigators will be expected to maintain an enrollment log for all patients enrolled in the study indicating their assigned study number. A patient will be considered enrolled upon assignment of a patient number. Each patient will sign an informed consent provided by the site.

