6.2.1 Study Entry

Principal investigator will hold the IND for the trial. All patients must be registered with the Clinical Trials Network and Monitoring Office of the UAB Comprehensive Cancer Center ([name], O.C.N.) before enrollment in study. Prior to initiation of therapy eligibility criteria must be confirmed. At the time of registration, a study identification number will be generated. All subsequent case report forms will use this study identification number.

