6.2.2 Pre-study Assessments

Informed consent will be obtained before study-specific screening evaluations are performed. Screening evaluations must be performed within 4 weeks prior to day 0.

Within the 4 weeks prior to therapy initiation patients will undergo baseline clinical evaluation (including history, physical evaluation, vital signs, and performance status) and all enrolled patients will undergo biopsy of a selected lesion according to the guidelines described in eligibility criteria. Additional pre-study evaluations include: CBC with differential and platelets, CMP (fasting), CA27.29, pregnancy test (within 7 days if indicated), tumor measurements by images or staging studies which are defined as studies contributing to response evaluation, e.g. CTs (chest, abdomen, and pelvis), MRI, bone scan, PET, or plain x-rays, EKG and echocardiogram, and concomitant medication assessment. The ejection fraction will be confirmed as normal before proceeding with the first dose of lapatinib.

Patients with reasonably accessible lesions as described above, who will not agree with the biopsy, will not be enrolled in the trial. Patients with NO reasonably accessible lesions as described above can be enrolled in the trial.

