6.2.3 Treatment and Assessments

Patients will not be randomized; patients will be treated as described before. For this pilot study, a course of therapy is 28 day. We are allowing a treatment window of \pm 1-3 days. Lapatinib will be administered before Veliparib. Patients will be restaged with the same images or staging studies used in the baseline evaluation (staging studies are defined as studies contributing to response evaluation, e.g. CTs (chest, abdomen, pelvis), MRI, bone scan, PET, or plain x-rays every 8 weeks (as an example, before course 3, 5, 7, 9, ..), and tumor response defined by RECIST criteria version 1.1. Patients with SD, PR or CR may continue therapy until disease progression or intolerance to therapy. An EKG will be obtained on day 2 and 3 of cycle one. Also, an EKG will be obtained on day one of each subsequent cycle. Echocardiogram will be obtained every 3 months.

In addition, patients will undergo performance status, CBC with differential and platelets, CMP, concomitant medication assessment; and assessment of adverse events on day 1 of each cycle. Hypocalcemia, hypokalemia, and hypomagnesemia will be corrected prior to lapatinib administration. Physical evaluation, vital signs, and weight will be performed day 1 of each cycle. CA27.29 will be obtained every 8 weeks. Pharmacokinetic samples are described in section 6.3.

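### The waiver of the Cycle 1 Day 1 CBC and CMP conflicts with section 6.2.3 and lets the eligibility and baseline sample predate the last chemotherapy dose by up to 7 days

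*Combined protocol and SAP*

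**What the plan says.** All references are to the combined protocol and SAP.

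- **6.6 Study Parameters, footnote 11**, attached to the CBC and CMP rows: "Cycle 1, Day1 CBC and CMP only need to be obtained if prior labs are greater than 4 weeks".
- **6.2.3 Treatment and Assessments**: "patients will undergo performance status, CBC with differential and platelets, CMP, concomitant medication assessment; and assessment of adverse events on day 1 of each cycle". There is no Cycle 1 exception.
- **6.2.2 Pre-study Assessments**: "Screening evaluations must be performed within 4 weeks prior to day 0".
- **4.1 Inclusion Criteria**, washout: "Chemotherapy treatment prior to enrollment must be discontinued for at least 3 weeks prior to study entry". The radiation rule in the same list is counted to the start of protocol treatment instead.
- **4.1**, recovery: "Patients must have recovered from all reversible toxicities related to prior therapy before beginning protocol treatment". The same section sets limits for neutrophils, hemoglobin, platelets, bilirubin, transaminases and creatinine.
- **6.2 and 6.2.1**: "A patient will be considered enrolled upon assignment of a patient number", and "Prior to initiation of therapy eligibility criteria must be confirmed". Neither defines study entry or limits the time from entry to first dose.

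No section requires the eligibility CBC and CMP to be drawn after the last chemotherapy dose, and none says which sample is the baseline.

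**The concern.** The permitted age of the blood tests (28 days) is longer than the minimum chemotherapy washout (21 days), and footnote 11 removes the only other CBC and CMP scheduled before dosing. A patient can meet every written laboratory requirement on a sample taken before her last chemotherapy dose. Marrow, liver and renal recovery after that dose would then be assumed without a test.

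Three parts of the safety analysis rest on a sound baseline:

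- item (b) of the toxicity definition in 3.0, 7.1 and 7.6, which counts a patient who does not return to baseline after a delay of more than 14 days;
- the summaries of baseline laboratory data and change at each visit in 7.5.1;
- the causality definitions at the end of section 9, which turn on whether another therapy sufficiently explains the event.

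If the baseline is too early, leftover chemotherapy toxicity may be counted against the combination, or real toxicity of the combination may be put down to chemotherapy.

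**Working it through.** **Inputs.** The limit on laboratory age is 28 days (6.2.2; 6.6 footnote 11). Day 0 is read as the start of therapy, because 6.2.2 goes on to count the 4 weeks to therapy initiation. The washout is 21 days, counted to study entry (4.1). Let k be the days from study entry to first dose; the documents give no value. N = 20 (7.4), and the boundary is Table 3 in 7.6.

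**1. The plan's own stopping-rule figures.** I used an exact binomial recursion over the printed boundary: after each patient, the probability of each toxicity count is carried forward and paths at or above X are removed.

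| True rate | P(stop early): plan / recomputed | Expected N: plan / recomputed | Expected toxicities: plan / recomputed |
|---|---|---|---|
| 30% | 0.10 / 0.098 | 18.87 / 18.87 | 5.7 / 5.66 |
| 60% | 0.87 / 0.872 | 9.8 / 9.76 | 5.9 / 5.86 |

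The rule performs as stated. The question is only which events are fed into it.

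**2. Overlap of the windows.** The earliest valid sample is on day −28. The latest permitted chemotherapy is on day −(21 + k). The sample can precede the last dose by max(0, 28 − (21 + k)) = max(0, 7 − k) days:

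- k = 0: 7 days
- k = 3: 4 days
- k = 6: 1 day
- k ≥ 7: none

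**3. Time to the next scheduled count.** The 6.6 table has no CBC or CMP on Day 8 or Day 15 of Cycle 1. With the waiver, the next one is Cycle 2 Day 1, which is 28 days after the first dose. Scheduled samples can thus be 28 + 28 = 56 days apart. The next scheduled count falls at least 21 + k + 28 = 49 + k days after the last chemotherapy.

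**4. What one patient is worth.** 1/20 = 5 percentage points. Clopper-Pearson 95% intervals:

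- 5/20: 8.66% to 49.10%
- 6/20: 11.89% to 54.28% (this and the 5/20 interval match the table in 7.4)
- 7/20: 15.39% to 59.22%

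**5. Sensitivity, on an assumption.** Let c be the share of patients with a carry-over event that is counted. The documents give no value for c. From a true 30% rate, the counted rate is 0.30 + 0.70c.

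| Assumed c | Counted rate | P(stop early) |
|---|---|---|
| 0 | 30.0% | 0.098 |
| 2% | 31.4% | 0.119 |
| 5% | 33.5% | 0.155 |
| 10% | 37.0% | 0.231 |

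These rows show how the rule would respond. They do not estimate what will happen.

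**The case against.** A reader might infer that residual cytopenia will be charged to the combination and will inflate the primary toxicity rate. The documents do not support that:

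- The endpoint counts drug-related toxicity only (3.0, 7.1, 7.6), and the causality definitions in section 9 answer no when another therapy sufficiently explains the event.
- Most uncomplicated cytopenia does not qualify. Neutropenia must come with fever or infection, or be grade 4 for at least 7 days. Thrombocytopenia must be grade 4, or grade 3 with hemorrhage.
- With no count scheduled until at least 49 days after the last chemotherapy, an earlier cytopenia would come to light only through a complication or an unscheduled test.
- The overlap needs recent chemotherapy and study entry fewer than 7 days before first dose. It cannot arise when the only chemotherapy was remote adjuvant or neoadjuvant treatment. Because consent must precede study-specific screening, it also needs consent before the last chemotherapy dose or reuse of routine laboratory results.
- Crossing the boundary at 3 of 3, 4 of 4 or 4 of 5 takes two or three other qualifying events, and the boundary is a guideline for a committee.

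All of this stands, and it limits the claim about the primary rate.

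Two further replies are weaker. First, footnote 11 can be read as a specific exception to a general rule, and it does not forbid a repeat test. But 6.2.3 signals no exception, so sites could follow either text, and a minimum that permits no test does not ensure one. Second, the 4.1 recovery rule and the 6.2.1 eligibility check already protect the patient. But a sample taken before the last chemotherapy satisfies the written check, and recovery of marrow, liver and kidney cannot be confirmed without a later test. The 6.2.3 instruction to correct low potassium and calcium before lapatinib does imply current chemistry. Yet the CMP that would show it is the panel waived; only magnesium is still scheduled on Day 1 without the footnote.

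**Conclusion.** The point holds as a gap in the schedule and an internal conflict. Footnote 11 and section 6.2.3 disagree on whether a Cycle 1 Day 1 CBC and CMP is required. If the footnote governs, the qualifying sample can predate the last chemotherapy dose by up to 7 − k days, at most 7, with nothing required afterwards before dosing. If 6.2.3 governs, the gap closes. The 7-day figure assumes that study entry and first dose fall on the same day.

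The consequence is an unreliable baseline and possible misattribution in either direction, worth 5 percentage points per misclassified patient. An actual bias in the primary rate is not shown. How often the situation would arise cannot be derived from the documents, and the carry-over shares in the sensitivity table are assumptions. The change is still worth making, because the gap affects eligibility checks as well as the primary safety endpoint and is cheap to close.

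**What to change.** Reconcile footnote 11 with 6.2.3 by removing the Cycle 1 waiver. State that a CBC and CMP must be obtained after the last prior anticancer therapy and before the first dose. Name that sample as the baseline for toxicity grading, for item (b) of the toxicity definition and for the laboratory changes in 7.5.1. The exact window before first dose is for the sponsor to set; the documents do not point to one value. With the sample tied to the last prior therapy, the undefined study entry no longer matters for this point.

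The cost is a wording change and one routine panel per patient, at a visit where blood is already drawn for pharmacokinetics, ptDNA, serum markers, magnesium and pharmacogenomics. An occasional start may be delayed. The sample size, boundary and analysis methods are unchanged.

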6.7 Efficacy and Safety Assessments

Response and progression will be evaluated in this study using the international criteria proposed by the Response Evaluation Criteria in Solid Tumors (RECIST) Committee; version 1.1 (see Appendix D).⁷⁵ Changes in only the largest diameter (unidimensional measurement) of the tumor lesions are used in the RECIST criteria. Note: Lesions are either measurable or non-measurable using the criteria provided below. The term “evaluable” in reference to measurability will not be used because it does not provide additional meaning or accuracy.

6.7.1 Definitions

Measurable Disease – Measurable lesions are defined as those that can be accurately measured in at least one dimension (longest diameter to be recorded) as ≥ 20 mm by chest x-ray, as ≥ 10 mm with CT scan, or ≥ 10 mm with calipers by clinical exam. All tumor measurements must be recorded in millimeters (or decimal fractions of centimeters).

Definitions proved for normal: short axis < 10 mm, Measurable (Target): short axis ≥ 15 mm, Non-measurable: short axis 10 to <15 mm, Target nodes measured in the short axis (perpendicular to longest diameter) more reproducible and predictive of malignancy. Short axes of target nodes to be added to the sum of longest diameters.

Non-Measurable Disease – All other lesions (or sites of disease), including small lesions (longest diameter <10 mm or pathological lymph nodes with >10 to <15 mm short axis, are considered non-measurable disease. Bone lesions, leptomeningeal disease, ascites, pleural/pericardial effusions, lymphangitis cutis/pulmonitis, inflammatory breast disease, and abdominal masses (not followed by CT or MRI), are considered as non-measurable

Target Lesions – All measurable lesions up to a maximum of two lesions per organ and 5 lesions in total, representative of all involved organs, should be identified as target lesions and recorded and measured at baseline. Target lesions should be selected on the basis of their size (lesions with the longest diameter), be representative of all involved organs, but in addition should be those that lends themselves to reproducible repeated measurements. It may be the case that, on occasion, the largest lesion does not lend itself to reproducible measurement in which circumstance the next largest lesion which can be measured reproducibly should be selected. A sum of the diameters (longest for non-nodal lesions, short axis for nodal lesions) for all target lesions will be calculated and reported as the baseline sum. If lymph nodes are to be included in the sum, then only the short axis is added to the sum. The baseline sum LD will be used as referenced by which to characterize the objective tumor response.

Non-Target Lesions – All other lesions (or sites of disease) including any measurable lesions over and above the 5 target lesions should be identified as **non-target lesions** and should also be recorded at baseline. Measurements of these lesions are not required, but the presence, absence, or in rare cases unequivocal progression of each should be noted throughout the follow-up.

All other lesions (or sites of disease) including any measurable lesions over and above the 5 target lesions should be identified as **non-target lesions** and should also be recorded at baseline.

Measurements of these lesions are not required, but the presence, absence, or in rare cases unequivocal progression of each should be noted throughout the follow-up.

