A tumor biopsy of one of the metastatic lesions (see eligibility criteria for biopsy guidelines) will be obtained before initiation of therapy. Biopsy samples will preferably be obtained using a 14-18 gauge core needle; **at least** two core biopsies will be obtained and snap frozen individually for gene expression; a **third** core will be used for the preparation of paraffin-embedded blocks or formalin fixed tissue.

Biopsy of a metastatic lesion is not required for protocol entry but all patients with reasonably accessible lesions (chest wall, breast, skin, subcutaneous, superficial lymph nodes, bones and liver metastases) must agree to biopsy. Lung biopsies are not acceptable for research only. Biopsies may be done with local anesthesia or intravenous conscious sedation, according to standard institutional guidelines. If a biopsy requires general anesthesia, then it is only allowed **if** acquisition of tissue is necessary for clinical reasons (i.e. is clinically indicated), and excess tissue that would otherwise

have been discarded is then used for research purposes. If a biopsy requires general anesthesia, then a biopsy of that site for research purposes only, *without* a coexisting clinical indication is not allowed on this protocol. Patients with reasonably accessible lesions as described above, who will not agree to the biopsy, will not be enrolled in the trial. Patients with NO reasonably accessible lesions as described above can be enrolled in the trial.

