6.7.2 Guidelines for Evaluation of Measurable Disease

General Aspects of Tumor Measurement - All measurements should be taken and recorded in metric notation using a ruler or calipers. All baseline evaluations should be performed as closely as possible to the beginning of treatment and never more than 4 weeks before the beginning of the treatment. Note: Tumor lesions that are situated in a previously irradiated area might or might not be considered measurable. The same method of assessment and the same technique should be used to characterize each identified and reported lesion at baseline and during follow-up. Imaging-based evaluation is preferred to evaluation by clinical examination when both methods have been used to assess the anti-tumor effect of a treatment.

Specific Methods of Tumor Measurement:

- **Clinical lesions** – Clinical lesions will only be considered measurable when they are superficial (e.g., skin nodules and palpable lymph nodes). In the case of skin lesions, documentation by color photography, including a ruler to estimate the size of the lesion, is recommended.
- **Chest x-ray** – Lesions on chest x-ray are acceptable as measurable lesions when they are clearly defined and surrounded by aerated lung. However, CT is preferable.
- **Conventional CT and MRI** – This guideline has defined measurability of lesions on CT scan based on the assumption that CT slice thickness is 5mm or less. If CT scans have slice thickness greater than 5mm, the minimum size for a measurable lesion should be twice the slice thickness. MRI is also acceptable in certain situations (e.g. for body scans).

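### Target-lesion selection has no exception for the lesion biopsied before treatment, and baseline measurement is not ordered relative to the biopsy, so procedure swelling can occasionally be scored as a partial response

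*Combined protocol and SAP*

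**What the plan says.** **Target selection.** Section 6.7.1 makes target lesions "All measurable lesions up to a maximum of two lesions per organ and 5 lesions in total", picked by size and to represent the organs involved. The only reason it gives for passing over the largest lesion is poor reproducibility of measurement, in which case "the next largest lesion which can be measured reproducibly should be selected". Biopsy is not mentioned.

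**Biopsy.** Section 6.2.2 states that, within the 4 weeks before therapy, "all enrolled patients will undergo biopsy of a selected lesion according to the guidelines described in eligibility criteria". Section 4.1 lists the accessible sites: "chest wall, breast, skin, subcutaneous, superficial lymph nodes, bones and liver metastases) must agree to biopsy". Patients with no accessible lesion may enrol without a biopsy, and lung and brain lesions are not biopsied. Section 6.3 asks for at least two frozen cores plus a third, and says "Biopsy samples will preferably be obtained using a 14-18 gauge core needle".

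**Timing.** Section 6.7.2 ties baseline measurement to the start of treatment: as close to it as possible and "never more than 4 weeks before the beginning of the treatment". The Section 6.6 table puts biopsy and staging in the same pre-treatment column. Neither section says which comes first.

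**Who can be exposed.** Section 4.1 requires only "at least one lesion that can be accurately measured in at least one dimension", so the biopsied lesion may be the sole target. Section 6.7.2 accepts superficial lesions, such as skin nodules and palpable nodes, as clinically measurable. Section 6.7.1 classes bone lesions as non-measurable.

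**Use of the result.** Section 6.7.3.1 defines partial response as a fall of at least 30% from the baseline sum. Section 7.4 says that a phase II trial will be proposed if the response rate is 30% or more.

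**The concern.** Apart from bone, the sites that must be biopsied can also hold target lesions. A patient with few lesions may therefore have the biopsied one in the baseline sum. If it is measured while swollen, the baseline sum is too large, and the return to true size looks like shrinkage caused by the drugs.

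The error favours response, and a single-arm trial has no control group to reveal it. A confirmatory scan would trim reading noise but would not correct the baseline. In any case, the footnote in Section 6.7.4 limits confirmation to trials with response as the primary endpoint, which this is not. With 20 patients, each responder is worth 5 percentage points of ORR.

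The plan comments on previously irradiated lesions (Section 6.7.2) but not on biopsied ones, and Appendix D is only a link.

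**Working it through.** **1. The plan's own figures.** The Clopper-Pearson limits in Section 7.4 reproduce: 4/20 gives 5.73-43.66%, 5/20 gives 8.66-49.10%, 6/20 gives 11.89-54.28%. They are not in dispute. The 30% rule means at least 6 responders of 20.

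**2. Swelling needed for a false partial response.** Take k equal target lesions, one biopsied, with true shrinkage t in all of them. Let f be the fractional inflation of the biopsied lesion at baseline. A 30% fall is scored when k(1 - t)/(k + f) = 0.7, so f = k(1 - t)/0.7 - k.

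| True shrinkage | 1 target | 2 targets | 3 targets | 5 targets |
|---|---|---|---|---|
| 0% | 43% | 86% | 129% | 214% |
| 20% | 14% | 29% | 43% | 71% |
| 25% | 7% | 14% | 21% | 36% |

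For a sole target with no shrinkage, f = 3/7 of its diameter: 4.3 mm for 10 mm, 5.1 mm for 12 mm, 6.4 mm for 15 mm.

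**3. Adding reading error.** Assumptions, none of them in the documents: reading SD 1 mm; swelling of 0, 2 or 3 mm at baseline only; true size constant; two follow-up scans, with a partial response if either sum is at most 0.7 of baseline; every target measured at 10 mm or more at baseline. With 400,000 draws, the no-effect partial response rates are:

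| Targets | No swelling | 2 mm | 3 mm |
|---|---|---|---|
| One, 10 mm | 2.6% | 17% | 37% |
| One, 12 mm | 0.3% | 7% | 19% |
| One, 15 mm | about 0% | 1% | 5% |
| One, 20 mm | 0% | 0.01% | 0.14% |
| Two, 10 mm each | 0.2% | 1.4% | 4.0% |
| Three, 10 mm each | 0.02% | 0.1% | 0.4% |

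If the 10 mm condition at baseline is dropped, the two-target rates with 2 and 3 mm of swelling are 0.8% and 2.3%.

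**4. Tissue removal.** Assume a spherical 10 mm lesion and three cores of 1.6 mm bore spanning it. Volume removed is 3 × π × 0.8² × 10 = 60.3 mm³ out of π × 10³/6 = 523.6 mm³, or 11.5%. The equivalent fall in diameter is 1 - 0.885^(1/3) = 4%. A 30% fall in diameter needs a volume loss of 1 - 0.7³ = 65.7%. Even six cores of 2.1 mm give only 15.5% of diameter.

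**5. Effect on the 30% rule.** Let m be the chance that one exposed patient, not a true responder, is scored as one. Then P(at least 6 of 20) = (1 - m) × P(Bin(20, p) ≥ 6) + m × P(Bin(19, p) ≥ 5).

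- p = 15%, m = 17%: 0.83 × 0.0673 + 0.17 × 0.1444 = 0.080, against 0.067.
- p = 20%, m = 17%: 0.83 × 0.1958 + 0.17 × 0.3267 = 0.218, against 0.196.
- m = 7%: 0.073 and 0.205.
- m = 37%: 0.096 and 0.244.

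**The case against.** **The rule leaves room for judgement.** An investigator can pass over a swollen lesion as not reproducibly measurable, and can biopsy a non-target lesion, since Section 6.2.2 says only that a selected lesion is sampled. This stands: the plan does not force the biopsied lesion into the sum in every patient. But it does not direct anyone away from that lesion, and the reproducibility clause does not help where there is no other measurable lesion.

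**The large rates are near a worst case.** They need a sole lesion at the 10 mm floor and 2-3 mm of swelling. Nodes need a short axis of at least 15 mm to be targets. Tumours may also grow: Section 2.1 cites a time to progression of 2.8 months in triple-negative disease on paclitaxel. If growth of 10% and 20% at the two scans is assumed, the 10 mm rates fall to about 2% and 7%. This also stands, and it is why the point is minor.

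**Stronger readings a reader might infer.**
- *False complete responses.* Resolved swelling leaves a non-nodal lesion present, whereas Section 6.7.3.1 requires disappearance. A false nodal response of this kind would need a node truly under 10 mm to measure 15 mm or more at baseline.
- *Shrinkage from tissue removal.* Step 4 shows that cores fall far short of 30%. Punch and excision biopsies do not appear in the documents. The word preferably may qualify only the gauge, and the one non-core opening is leftover tissue from a clinically indicated procedure under general anesthesia.
- *A large shift in the phase II decision.* A move from 0.067 to 0.144, or from 0.196 to 0.327, assumes that a false responder is certain to occur. Step 5 gives the unconditional figures for one exposed patient.

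**ORR is secondary.** Safety is primary, and the 30% rule leads only to a proposal. Sections 2.7 and 3.0 say, without any response condition, that the data will be used to design the phase II trial. This stands as a limit on severity.

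**Conclusion.** The gap is real but minor. The selection rule can put a procedure-inflated lesion into the baseline sum, and no other section prevents it. The result is a possible false partial response. The risk lies mainly where a small biopsied lesion is the only or dominant target, or where true shrinkage is just under 30%.

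Under the stated assumptions the no-effect rate runs from 17-37% in the most exposed patient (sole 10 mm target) to near zero with larger or more numerous targets. One such patient at 17% adds about 0.013 to 0.022 to the probability of meeting the 30% rule at true response rates of 15% and 20%. The frequency of such patients and the amount of swelling are not in the documents, so no overall bias in ORR can be given. The primary safety analysis, the sample size and the confidence intervals are unaffected.

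**What to change.** Add to Section 6.7.1: *The lesion biopsied before treatment is not selected as a target lesion when another measurable lesion is available; it is followed as a non-target lesion. If it is the only measurable lesion, its baseline measurement is taken before the biopsy.*

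Measuring before the biopsy leaves only the core-tissue loss of about 4% of a 10 mm diameter, which is small beside the swelling that it avoids.

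Record on the case report form which lesion was biopsied. In Section 7.5.2, report ORR with and without patients whose response depends on a biopsied target lesion.

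Cost: two sentences, one form field and one sensitivity line, with no extra patient, scan or procedure. The downside is slightly fewer target lesions in patients with limited disease.
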